## 7.1 Study subjects

#### 7.1.1 Disposition of subjects

The number and percentage of subjects screened, randomized, completed, discontinued, and the primary reason for discontinuation based on the CRF exit form will be displayed.

In addition, the number and percentage of subjects in each study population (i.e., ITT, ITTT, SAF, SAFT, PP, and PPT) will be summarized by treatment group as well as by center.

#### 7.1.2 Demographics and baseline characteristics

The following demographics variables will be summarized for the ITT population for each treatment group: age, Ethnicity, Race, Skin phototype, gender, and country of origin (US, EU, Russia). Age will be analyzed as a continuous variable and will be tabulated by age groups of "< 18 years" ("9-11 years", "12-14 years", "15-17 years"), and ">= 18 years" ("18-64 years", ">=65 years").

Baseline IGA, PGA, facial lesion counts (inflammatory and non-inflammatory), and truncal lesion counts (inflammatory and non-inflammatory) will be summarized by treatment groups.

Galderma R&D RD.06.SPR.18252 Page 13 of 25

# 7.2 **Protocol deviations**

Number and percentage of subjects with major protocol deviations will be summarized for each treatment group in the ITT population. A listing of subjects with major protocol deviations will also be provided.

#### 7.3 Medical history, previous and concomitant therapies/procedures

For statistical analysis purpose, previous therapies/procedures are defined as those ending at Baseline visit or before; and concomitant therapies/procedures are defined as those ongoing at the Baseline visit or starting after the Baseline visit.

Previous and concomitant therapies will be coded using WHODRUG dictionary). Previous and concomitant procedures will be coded using MedDRA dictionary.

A summary table will be provided for each of the following in the ITT population:

- 1. number and percentage of subjects who had previous therapies/medications by ATC text and WHO drug name
- 2. number and percentage of subjects who had concomitant therapies/medications by ATC text and WHO drug name
- 3. number and percentage of subjects who had previous procedures by System organ class and preferred term
- 4. number and percentage of subjects who had concomitant procedures by System organ class and preferred term

### 7.4 Efficacy analysis

#### 7.4.1 Efficacy analysis methods

Table 1 summarizes the efficacy endpoints analyses.

## 7.4.1.1 Analysis of the Primary Efficacy Endpoint

#### Hypothesis testing

Formally stated the hypotheses to be tested for the primary efficacy endpoint are:

IGA Success Rate, Ho:  $P_{\cdot CD5789} = P_{\cdot Vehicle}$ ,

Ha: P• CD5789  $\neq$  P•Vehicle

Where P. is the proportion of subjects in each treatment group from the overall population, who achieved the defined success criteria.

Galderma R&D RD.06.SPR.18252 Page 14 of 25

Change in facial Inflammatory and non-inflammatory lesions,

Ho:  $\delta_{\bullet \text{ CD5789}} = \delta_{\bullet \text{ Vehicle}}$ 

Ha:  $\delta_{\bullet \text{ CD5789}} \neq \delta_{\bullet \text{ Vehicle}}$ 

Where  $\delta_{\bullet}$  is the difference from baseline to week 12 for each treatment group from the overall population, in facial inflammatory and non-inflammatory lesion counts.

Endpoint	Primary vs. Supportive Approach †	Statistical Method	Analysis Population	Missing Data Approach
Co-Primary				

 
Success rate at week 12 (IGA)
 
	Р	CMH, ANCOVA	ITT	MI

 
Change from baseline of facial inflammatory
 
	S	CMH, ANCOVA	PP	MI
lesion counts at week 12	S	CMH, ANCOVA	ITT	MI (MNAR)
Change from baseline of facial non-	S	CMH, ANCOVA	ITT	LOCF
inflammatory lesion counts at week 12	S	CMH, ANCOVA	ITT	Missing as Failure
Co-Secondary	· · · · · · · · · · · · · · · · · · ·			

 
Success rate at week 12 (PGA)
 
	Р	CMH, ANCOVA	ITTT	MI
Change from baseline of truncal inflammatory	S	CMH, ANCOVA	PPT	MI
lesion counts at week 12	S	CMH, ANCOVA	ITTT	MI (MNAR)

 
Change from baseline of truncal non-
 
	S	CMH, ANCOVA	ITTT	LOCF
inflammatory lesion counts at week 12	S	CMH, ANCOVA	ITTT	Missing as Failure
Supportive	1	I		

 
Percent change from baseline in facial inflammatory lesion counts at week 12
 
Percent change from baseline in facial non- inflammatory lesion counts at week 12)
 
	Ρ	CMHS	ITT	MI

 
Percent change from baseline in truncal inflammatory lesion counts at week 12
 
Percent change from baseline in truncal non- inflammatory lesion counts at week 12)
 
	Р	CMHS	ITTT	MI

 
Subjects' assessment of facial acne improvement at week 12
 
	Р	CMHS	ITT	As Observed

† P=Primary approach; S=Supportive approach ITT = Intention to Treat, ITTT = Intention to Treat for the truncal acne; PP = Per Protocol on the face; PPT = Per Protocol on the trunk; MI = Multiple imputation using the missing at random assumption; MI (MNAR) = Multiple imputation using the missing not at random assumption; LOCF=Last

Galderma R&D RD.06.SPR.18252 Page 15 of 25

Observation Carried Forward. CMH: Cochran-Mantel-Haenszel test stratified by analysis center. CMHS: Cochran-Mantel-Haenszel test stratified by analysis center using the RIDIT score. ANCOVA: Analysis of Covariance model including treatment, analysis center, and baseline lesion count as factors.

As the primary efficacy endpoint consists of 3 co-primary endpoints, all of which need statistical significance for the primary efficacy endpoint to be successful, there is no need for Type I error adjustment for the multiple comparisons of the 3 co-primary efficacy endpoints.

The study will be declared positive if the two-sided p-values is statistically significant (< 0.05) for the difference between the 2 treatment groups in all 3 co-primary efficacy endpoints, and the superiority of CD5789 50  $\mu$ g/g to Vehicle will be established.

#### Statistical method

• IGA Success Rate:

Success rate at Week 12 based on the IGA will be analyzed using the Cochran Mantel Haenszel (CMH) test stratified by analysis center (see definition in Section 7.4.2.4). The primary analysis will be performed using the overall ITT population based on the Multiple Imputation methodology (MI) as the primary imputation method for missing values, see Section 7.4.2.2.

The p-value for the treatment comparison will be generated from the general association statistic of the stratified CMH test. Difference in success rate between treatment groups (CD5789 50  $\mu$ g/g – Vehicle) and the 95% confidence interval of the difference will be based on the large sample approximation method for binary data. The success rate for each treatment group will also be displayed for the overall ITT population.

The treatment-by-analysis center interaction for success rate will be assessed for the overall ITT population by using the pair-wise Breslow-Day tests for homogeneity of the odds ratio across analysis centers at Week 12 at alpha level of 0.10. The consistency of the treatment effect across analysis centers will be evaluated using descriptive statistics and using graphical methods.

Facial Lesion Counts:

Changes from baseline in facial lesion counts at Week 12 will be analyzed separately by type (inflammatory and non-inflammatory) using an ANCOVA (Analysis of Covariance) model including baseline count, analysis center, and treatment as factors. The primary analysis will be performed using the overall ITT population using the primary imputation method for missing values.

The p-value for the treatment comparison, estimate of the LSMEANS treatment difference (CD5789 50  $\mu$ g/g – Vehicle), and the 95% confidence interval of the LSMEANS difference will be generated from the ANCOVA model.

The treatment-by-analysis centers and the treatment-by-baseline lesion counts interactions for Change in Lesions Counts will be assessed separately by the interaction term at Week 12 at alpha level of 0.10 for the overall ITT population. The consistency of the treatment effect across

Galderma R&D RD.06.SPR.18252 Page 16 of 25

analysis centers will be evaluated using descriptive statistics and using graphical methods. The consistency of the treatment effect by baseline lesion counts will be evaluated using graphical methods.

In addition, change in Lesions Counts will be summarized descriptively at each visit for the overall ITT population.

#### Sensitivity analyses

The above primary efficacy analysis will be repeated using the PP population using the primary multiple imputation method for missing values.

To assess the robustness of the primary efficacy result, the following sensitivity analyses will be conducted for each of the 3 co-primary efficacy endpoints (see Section 4.1) using the ITT population:

a. The same imputation method above will be repeated based on the Pattern-Mixture Model under the missing not at random (MNAR) assumption, by using the profiles from vehicle subjects with observed data to impute missing data.

b. LOCF (Last observation carry forward) approach

c. Subjects with missing IGA data at Week 12 will be considered as 'failures' for IGA success rate; and subjects with missing lesion counts data at Week 12 will be assigned the median change of lesion counts data from subjects who are 'failures' of IGA success within the same treatment group.

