# 6 SAMPLE SIZE CONSIDERATION

The assumptions used to power this study are based on the Phase 2 study (SPR.18223) on the Non-Japanese population. Success rates based on IGA are assumed 23% (CD5789) and 15% (Vehicle). For a 90% power to detect a significant difference versus vehicle using a two-sided test at a type I error of 0.05, 504 subjects per arm are needed for analysis.

Based on the results from statum 1 in the phase 2 study (SPR18223), the mean difference between the active and vehicle is estimated at 3 inflammatory lesions and 6 non-inflammatory lesions. Standard deviation of changes in lesion counts, based on phase 2 and on large phases 3 trials from other projects are estimated at 12 for inflammatory lesions and 20 for non-inflammatory lesions. Using these as assumptions and a sample of 504 evaluable subjects per arm, power is 95% at least for both lesion types.

Galderma R&D RD.06.SPR.18252 Page 12 of 25

To compensate for drop-outs and non-evaluable subjects (estimated at 16%), a total of 1200 subjects are to be randomized into each treatment group in a 1:1 ratio stratified by center, with 600 subjects in each treatment group randomized.

The assumptions for truncal acne being the same as for facial acne in terms of efficacy, therefore it is estimated that the power for truncal acne is adequate.

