c. Subjects with missing IGA/PGA data at Week 12 will be considered as 'failures' for IGA/PGA success rate; and subjects with missing lesion counts data at Week 12 will be assigned the median change of lesion counts data from subjects who are 'failures' of IGA/PGA success within the same treatment group.

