#### 6.6. Missing as Failure Analysis of Lesion Counts

The missing-as-failure analysis will be used for lesion counts to impute missing lesion count change from baseline at week 12.

For missing facial lesion count data, the median change from baseline in lesion counts from among all observed IGA failures at Week 12 will be substituted. For missing truncal lesion count data, the median change from baseline in lesion counts from among all observed PGA failures at Week 12 will be used.

In both cases the median will be calculated separately for each treatment group, using actual treatment, and the imputation will use the median that corresponds to the treatment group of the subject being imputed.

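### The missing-as-failure analysis of lesion counts imputes each arm's own failure median, so it likely keeps most of the drug effect and is not the conservative check its label implies

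*SAP*

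**What the plan says.** SAP 7.4.1.1 lists three missing-data sensitivity analyses, meant to test the robustness of each of the three co-primary results in the ITT population: (a) multiple imputation from vehicle profiles under MNAR, (b) LOCF, and (c) the approach that Table 1 labels Missing as Failure.

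Item (c) has two halves. A missing Week 12 IGA counts as failure in both arms. A missing lesion count is "assigned the median change of lesion counts data from subjects who are 'failures' of IGA success within the same treatment group".

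Section 7.4.2.2 repeats this for face and trunk: "assigned the median change of lesion counts data from subjects who are 'failures' of IGA/PGA success within the same treatment group". Section 7.4.1.2 carries the same sensitivity analyses over to the co-secondary trunk endpoints. Section 6.6 of the October 2017 addendum keeps the rule and makes it explicit: the median is computed by arm, and "the imputation will use the median that corresponds to the treatment group of the subject being imputed".

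**The concern.** For IGA and PGA the label fits: a missing subject receives the same unfavourable outcome whichever arm they were in. For lesion counts the imputed value depends on the arm. Missing the IGA success criterion is not the same as having no lesion response. Most subjects in both arms are expected to miss it, so the failures are the typical subjects of their arm. If the drug lowers lesion counts generally, the failure median on active will be lower than on vehicle, and the imputation hands that difference back to the subjects who left.

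At stake is how this row is read for two of the three co-primary and two of the three co-secondary endpoints. A result that agrees with the primary analysis would look like survival of a harsh assumption, when the assumption contains much of the effect being tested.

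**Working it through.** **Inputs from SAP section 6.** IGA success 23% on CD5789 and 15% on vehicle, so 77% and 85% failures. For lesions, "the mean difference between the active and vehicle is estimated at 3 inflammatory lesions and 6 non-inflammatory lesions"; the standard deviations of change "are estimated at 12 for inflammatory lesions and 20 for non-inflammatory lesions". Evaluable 504 per arm; 16% loss; 600 randomized per arm.

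**The plan's own figures reproduce.** Two-sided 0.05, 90% power, pooled variance: n = [1.96·√(2·0.19·0.81) + 1.282·√(0.23·0.77 + 0.15·0.85)]² / 0.08² ≈ 503.3, so 504. Power at 504 per arm is 97.8% (3, SD 12) and 99.7% (6, SD 20), in line with the stated minimum of 95%. 504/0.84 = 600.

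**Assumptions not in the documents.** Lesion change is normal, and success is a cut on a latent normal variable correlated r with lesion improvement. Central range r = 0.3 to 0.7. The vehicle mean is set to 0, since only differences matter. Baseline and centre adjustment are ignored.

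**Step 1: failure medians.** With success probability p, the failure median is (arm mean) + SD·q, where q solves P(Z ≤ q and failure) = 0.5(1 − p). For active and vehicle, q is 0.117 and 0.081 at r = 0.3; 0.190 and 0.130 at r = 0.5; 0.253 and 0.170 at r = 0.7. The difference between arms is D = effect − SD·(q_active − q_vehicle). For example, at r = 0.5: 3 − 12·0.060 = 2.28.

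| D (share of effect) | r = 0.3 | r = 0.5 | r = 0.7 |
|---|---|---|---|
| Inflammatory, of 3 | 2.57 (86%) | 2.28 (76%) | 2.00 (67%) |
| Non-inflammatory, of 6 | 5.28 (88%) | 4.80 (80%) | 4.33 (72%) |

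At r = 0 the share is 100%; at r = 0.9 it is 59% and 66%.

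**Step 2: resulting treatment difference.** With the same fraction m missing in each arm:
- planned rule: (1 − m)·effect + m·D; at m = 0.16, r = 0.5: 0.84·3 + 0.16·2.28 = 2.88
- one vehicle-based value in both arms: (1 − m)·effect; 0.84·3 = 2.52

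With unequal fractions m_A and m_V:
- planned rule: effect − m_A·SD·q_active + m_V·SD·q_vehicle; at 20% and 12%, r = 0.5: 3 − 0.46 + 0.19 = 2.73
- vehicle-based value: (1 − m_A)·effect − (m_A − m_V)·SD·q_vehicle; 2.40 − 0.12 = 2.28

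| Missing, active / vehicle | Planned rule, of 3 | Planned rule, of 6 | Retained, planned | Retained, vehicle-based |
|---|---|---|---|---|
| 16% / 16% | 2.93 to 2.84 | 5.88 to 5.73 | 95–98% | 84% |
| 8% / 8% | 2.97 to 2.92 | 5.94 to 5.87 | 97–99% | 92% |
| 20% / 12% | 2.84 to 2.64 | 5.73 to 5.39 | 88–95% | 75–78% |

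Ranges run from r = 0.3 to r = 0.7. The 8% and the 20%/12% rates are assumed.

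**Step 3: standard error.** A constant adds almost no spread. Variance per arm is (1 − m)·SD² + m(1 − m)·(SD·q)². At m = 0.16, r = 0.5:
- inflammatory: √[(121.66 + 121.29)/600] = 0.636, against 12·√(2/504) = 0.756 for 504 completers per arm. Test statistic 2.88/0.636 = 4.53, against 3/0.756 = 3.97.
- non-inflammatory: 1.061 against 1.260. Test statistic 5.48 against 4.76.

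Under the plan's own assumptions, this analysis is more likely to reach p < 0.05 than an analysis of the completers alone.

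**The case against.** The strongest reply is that the stress test is already planned. Item (a) imputes missing values from vehicle data for all three co-primary endpoints, and 7.4.1.2 extends it to the trunk. A reader might infer from item (c) that lesion-count robustness goes untested; the documents do not support that. Nor does item (c) affect the success decision, which rests on the primary ITT analysis. This stands, and it confines the point to the lesion-count half of item (c).

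A reader might also infer that active dropouts are credited with the full 12-week benefit. The figures do not say so: it is 67 to 88% under the assumed correlations. Even that is a model result, because the documents give no lesion change by IGA status. The share would be small only if the drug's lesion effect were concentrated among IGA successes.

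The rule is not wholly lenient either. It gives each arm's missing subjects less improvement than that arm's average, so it costs the arm that loses more: 88 to 95% is retained at 20% versus 12% loss. The plan's 16% also covers non-evaluable subjects, some of whom may have Week 12 data, so actual missingness in the ITT population could be lower and the contrast smaller.

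Finally, failure has no natural value for a continuous outcome, and placing a dropout among the failures of their own arm is a prespecified, consistent reading. It is defensible as a description, but it does not make the lesion half comparable with the IGA half under the same label. A change of value alone also leaves the standard error too small: at 16% missing and r = 0.5, power for inflammatory lesions is 99.5% under the planned rule and 97.6% with a vehicle-based value.

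**Conclusion.** The point holds for the lesion-count half of item (c), face and trunk, as a minor improvement to a supportive analysis. The own-arm median builds a between-arm difference into the imputed values, and the constant narrows the standard error. The row therefore should not be read as a conservative check on lesion counts, though the IGA/PGA half does what its name says. The size depends on an assumed correlation of 0.3 to 0.7, a normal model, and the effects and standard deviations in SAP section 6. The trunk figures rest on the plan's statement that truncal assumptions equal the facial ones. The primary analysis and the success rule are unaffected.

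**What to change.** In item (c) of SAP 7.4.1.1 and 7.4.2.2, and in section 6.6 of the addendum, replace the own-arm median by one value for both arms: the median Week 12 change among observed vehicle-arm IGA failures (PGA failures for the trunk). Add a sentence saying that single-value imputation understates the standard error, so item (a) remains the main stress test for lesion counts. Because item (a) carries that weight, its lesion-count example code in addendum 6.3 deserves a separate check: it lists Week 8 twice and omits Week 4.

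The cost is one phrase in each place, one added sentence and one line of code. The downside is a supportive estimate less favourable to CD5789: 2.52 rather than 2.84 to 2.93 inflammatory lesions, and 5.04 rather than 5.73 to 5.88 non-inflammatory, at 16% missing per arm. The fix removes the built-in difference between arms but not the understated variance.

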#### 7.4.1.2 Analysis of the Secondary Efficacy Endpoint

The same statistical methods planned for the 3 co-primary efficacy endpoints will be used for the analyses of the 3 co-secondary efficacy endpoints using the overall ITTT population, with Multiple Imputation (MI) as primary imputation method for missing values (see Section 7.4.2.2).

If the superiority of CD5789 50  $\mu$ g/g to Vehicle is established for the primary efficacy endpoint, then CD5789 50  $\mu$ g/g will be declared superior to Vehicle in the secondary efficacy endpoint for the overall ITTT population if the two-sided p-value is statistically significant (< 0.05) for the difference between the 2 treatment groups in all 3 co-secondary efficacy endpoints.

As the testing of secondary efficacy endpoint is conditional on the success of primary efficacy endpoint, and all of the 3 co-secondary efficacy endpoints need statistical significance for the secondary efficacy endpoint to be successful, no Type I error adjustment is needed for the multiple comparisons of the 3 co-secondary efficacy endpoints.

The above secondary efficacy analysis will be repeated using the PPT population with the primary multiple imputation method for missing values.

Galderma R&D RD.06.SPR.18252 Page 17 of 25

The same sensitivity analysis methods to handle missing data planned for the primary efficacy endpoint will also be applied for the analyses of the secondary efficacy endpoint in the overall ITTT population.

# 7.4.1.3 Analysis of the Supportive Efficacy Endpoints

No Type I error adjustment will be needed for the analyses of the supportive efficacy endpoints.

Facial Lesion Counts:

The analyses of Percent Change in facial lesion counts by type (Inflammatory Lesion Count and non-inflammatory lesion count) will be performed by the Cochran-Mantel-Haenszel test (CMH) stratified by analysis center. The analyses will be carried out in the overall ITT population with the primary multiple imputation methodology for missing data (see Section 7.4.2.2).

The p-value will be from the row mean difference statistic of the CMH test using RIDIT score.

In addition, percent change in facial lesion counts by type will be summarized descriptively by visit.

• Truncal Lesion Counts:

The same analysis method planned for the facial lesion counts will be used for the analyses of Percent Change in truncal lesion counts using the overall ITTT population.

• Subjects' assessment of facial acne improvement:

The analysis of the subjects' assessment of facial acne improvement will be based on the overall ITT population using observed data at Week 12 (i.e., no missing data imputation).

The p-value will be from the row mean difference statistic of the CMH test using RIDIT score.

In addition, the number and percent of subjects will be summarized for each treatment group by each scale of improvement.

# 7.4.2 Statistical and analytical issues

This section is intended to be completed by actual results during CSR writing.

# 7.4.2.1 *Adjustment for covariates*

The analysis of change from baseline in lesion counts will use an adjustment for the number of baseline lesions as described in Section 7.4.1.1.

# 7.4.2.2 Handling of dropouts or missing data

The primary method of imputation for missing data will be MI (Multiple Imputation) using the Missing At Random (MAR) assumption.

Galderma R&D RD.06.SPR.18252 Page 18 of 25

For the primary MAR based multiple imputation, the MI procedure of the SAS system will be used to generate sets of data with missing values imputed from observed data. It is expected that the pattern of missing data will be monotonic, with slight deviations being corrected by the Markov Chain Monte Carlo (MCMC) method of the MI procedure.

Linear regression will be employed to model the missing lesion count data and a logistic regression model will be used for the ordinal IGA/PGA scores, with the following covariates included in the imputation model: treatment and non-missing data from earlier timepoints. IGA/PGA success will be calculated from the imputed IGA/PGA scores. The imputed datasets will be analyzed using the methodology described in Section 7.4.1.1 for changes in lesion counts, and IGA/PGA success. The results from the analysis of the multiple imputed datasets will be combined by the MIANALYZE procedure of the SAS system. The seed number to be used will be the protocol number (18252) and the number of imputation is planned to be 5.

For success rate, the final p-value from the CMH test stratified by analysis center on each multiply imputed dataset will be generated using the Schafer, J. L. Multiple Imputation Methodology. The final difference of success rate between treatment groups (CD5789 50  $\mu$ g/g – Vehicle) and the final 95% confidence interval of the difference from each multiply imputed dataset will be generated using the method by Bohdana Ratitch ed. al..

For changes in lesion counts, the final p-value, treatment difference (CD5789 50  $\mu$ g/g – Vehicle), and the 95% confidence interval of the treatment difference from the ANCOVA model on each multiply imputed dataset will be generated from the MIANALYZE procedure of SAS.

To assess the robustness of the primary efficacy results, the following sensitivity analyses will be also conducted:

a. The same imputation method above will be repeated based on the Pattern-Mixture Model under the missing not at random (MNAR) assumption, by using the profiles from vehicle subjects with observed data to impute missing data.

b. LOCF (Last observation carry forward) approach

c. Subjects with missing IGA/PGA data at Week 12 will be considered as 'failures' for IGA/PGA success rate; and subjects with missing lesion counts data at Week 12 will be assigned the median change of lesion counts data from subjects who are 'failures' of IGA/PGA success within the same treatment group.

